4.4 Sample size

This is the first study that investigates the functional outcome effect of motor imagery training during the immobilization period in DRF-patients. Therefore, the sample size calculation cannot be based on data of an imagery intervention during immobilization on function after a DRF. In this study, function is the primary outcome variable, and it is measured using the Patient Rated Wrist/Hand Evaluation (PRWHE). This instrument is derived from the Patient Rated Wrist Evaluation (PRWE). The only difference between the PRWE and PRWHE is that the PRWHE contains extra questions about aesthetics. It still contains the originally validated questions,

format and scoring system. The added questions about aesthetics are not part of the scoring. Therefore, it can be treated as the PRWE (59). The PRWE is proven to be the most responsive instrument to measure outcome in DRF-patients (60), as it measures disability during usual and specific activities and also documents pain. Subjects can score from 0 to 100 on the PRWHE; 0 indicates no problems at all and 100 indicates large functional difficulties and severe pain. The sample size calculation will be based on the expected outcomes of motor imagery training on the PRWHE.

Description of calculation process

A previous study has described the change of the PRWE-score over time as a result of the process of natural recovery after a DRF (61). Based on the results of this study, a mathematical model was created using Matlab R2010a that estimates the PRWHE-scores between data collection moments. This way, a model was build to estimate the natural recovery process with respect to the outcome of the PRWHE. Using this model, it could be determined what the decrease of the PRWHE-score is, two weeks after cast removal. The results of this model showed that a decrease of 10 points can be expected between the first (T1) and second measurements (T2). This decrease is due to natural recovery, and therefore, we expect it to be present in both groups.

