Grip strength is important for the execution of many occupational activities (72). It is measured using a hydraulic dynamometer, which is found to be reliable and valid (73). Research has shown that the position of the wrist can influence the maximal grip strength that can be applied. This is especially the case when the wrist is in ulnar or radial deviation, which is one of the deformities that is common after a DRF malunion (74). Therefore, it is useful to determine different grip strengths; grasp, tip pinch, key pinch, and three-jaw chuck pinch (72,73). The measurements will be conducted using a standardized protocol (73), to counter the effects of confounders. The mean of three trials has the highest test-retest reliability (73), and therefore, it is decided to measure the strength of each grip three times. To control for within-group variability, grip strength is measured on both hands.

Two dimensions of pain are measured using a Visual Analog Scale (VAS) (75); pain intensity and pain relief (76). This results in a score between 0 and 100, where 0 represents severe pain and low pain relief, and 100 represents no pain and large pain relief.

7.1.3 *Other study parameters*

Confounding factors that might influence the dependent variables are age, motor imagery ability, type of fracture, occupation, sport activities and involvement of their casted hand in activities. The patients will be asked for their occupation, sport activities and involvement of the

casted hand in activities. The confounding factors will be included in the statistical analysis as covariates to control for their influence.

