9. STATISTICAL ANALYSIS

9.1 *Descriptive statistics*

Patient characteristics are presented using descriptive statistics for the potential confounding variables.

Data of the main outcome measure are of interval level of measurement. The ROM and grip strength are of ratio level of measurement. Hence, the descriptive statistics of these outcome measures are presented by the mean and standard deviation. Dexterity is measured using the SODA, and the data of this instrument are of ordinal level of measurement. Therefore, the descriptive statistics are presented by the median and range. Pain is measured using the VAS, which provides data of interval level of measurement. So, the descriptive statistics are presented by the mean and standard deviation.

9.2 *Univariate analysis*

The effectiveness of motor imagery training will be determined with use of a multivariate analysis for the parametric data (as described later in chapter 9.3). The non-parametric data are analyzed using a Mann-Whitney U test for each variable, to determine whether the groups are different. This test is also used when the data is not normally distributed.

9.3 *Multivariate analysis*

With use of a MANOVA, the difference between the experimental and control group will be determined for each measurement time and for each variable. There are two factors included in the analysis; a between factor 'group' and a within factor 'time'. The hypothesis is tested using two-tailed tests, with a significance level of 5%. The data of the patients in both groups will be analyzed using an intention to treat analysis.

9.4 *Interim analysis (if applicable)*

An interim analysis will be conducted to determine the effect of motor imagery training on hand function, dexterity, ROM, grip strength and pain. When the results of this analysis shows serious unwanted effects of motor imagery training, this study will be terminated.

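### The normality switch in section 9.2 lets an undefined look at the data decide which test, and which hypothesis, is primary for the PRWHE

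*Combined protocol and SAP*

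**What the plan says.** Section 9.2 sorts outcomes by data type. For one class, "The effectiveness of motor imagery training will be determined with use of a multivariate analysis for the parametric data", meaning the MANOVA of section 9.3. For the other, "The non-parametric data are analyzed using a Mann-Whitney U test for each variable, to determine whether the groups are different". It then adds: "This test is also used when the data is not normally distributed".

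Section 9.1 puts the PRWHE in the first class: "Data of the main outcome measure are of interval level of measurement". The primary outcome therefore starts in the 9.3 model and can leave it only through that last sentence of 9.2.

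On the model itself, section 9.3 states: "There are two factors included in the analysis". These are group (between patients) and time (within patients). The same section also promises a group difference at each measurement time.

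Section 7.1.3 names age, motor imagery ability, fracture type, occupation, sport and use of the casted hand as confounders, and says: "The confounding factors will be included in the statistical analysis as covariates to control for their influence". Section 4.4 derives the 52 patients from the within-between interaction of a repeated-measures ANOVA with two groups and two measurements.

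**The concern.** The switch sentence does not say how non-normality is judged: by which test, at what threshold, on raw data or residuals, or by arm and visit or pooled. It also does not say what the Mann-Whitney test is then applied to: T1 (cast removal), T2 (two weeks later) or the change between them. Two careful analysts could follow the plan and report different primary tests.

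The branches also ask different questions. The sample size is for a difference in change between arms. A Mann-Whitney test at one visit asks whether the arms differ at that visit. It has no within-patient factor and no covariates, and 9.2 attaches no estimate to it, although section 4.4 sets the target difference in PRWHE points.

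Non-normality is a realistic prospect: "Subjects can score from 0 to 100 on the PRWHE", so the score is bounded. Raw non-normality is also a poor trigger, because a linear model relies on the behaviour of its residuals. Loss of adjustment deserves attention here because allocation precedes consent and section 7.2 reports response rates of 35% and 62% in the two arms, so those who enrol may not be balanced.

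**Working it through.** **1. The two branches side by side**

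| | Section 9.3 model | Mann-Whitney under 9.2 |
|---|---|---|
| Within-patient time factor | yes | cannot hold one |
| 7.1.3 covariates | could hold them; 9.3 lists none | cannot hold them |
| Visit or contrast | group by time, and each visit | not stated |
| PRWHE difference with interval | obtainable from the model | none planned |

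**2. Reproducing the plan's figure.** Inputs from section 4.4: f = 0.20, k = 2 groups, m = 2 measurements, alpha 5%, power 80%. The visit correlation is not printed (other settings were left at default); I assume rho = 0.5. For the interaction, lambda = f² × N × m / (1 − rho), with 1 and N − 2 degrees of freedom.

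- N = 52: lambda = 0.04 × 52 × 2 / 0.5 = 8.32, power 0.807.
- N = 50: lambda = 8.00, power 0.791.

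The smallest even N reaching 80% is 52, as stated. The planned size therefore belongs to the interaction test.

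The matching difference in change follows from lambda. At rho = 0.5 the SD of change is SD × √(2 × 0.5) = SD, so with 26 per arm lambda = delta² × 26/2 = 13 delta². Then delta² = 8.32/13 = 0.64 and delta = 0.8 SD, or 0.8 × 26.13 = 20.9 points. The illustration uses this value because it is where 52 patients give about 80% power. It is not the plan's own difference, 5.3/26.13 = 0.20 SD; that discrepancy is a separate matter.

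**3. How often the switch fires.** The plan gives no trigger. I assume Shapiro-Wilk at 5% in each of the four arm-by-visit cells, any one failing. For truly normal data and independent checks, 1 − 0.95⁴ = 18.5%. Simulation (26 per arm, rho = 0.5, 4,000 trials) gives about 19%. A right-skewed bounded score gives about 80%, and lognormal data over 99%.

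**4. What the branch does to the result.** Rejection rates from the same simulation; the switch rule uses the interaction test, or Mann-Whitney at T2 if the trigger fires.

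| Scenario | Interaction | Mann-Whitney, T2 | Mann-Whitney, change | Switch rule |
|---|---|---|---|---|
| No effect, normal | 5% | 5% | 5% | 5% |
| 0.8 SD at T2 only, normal | 81% | 79% | 78% | 81% |
| 0.8 SD at both visits, normal | 5% | 79% | 5% | 20% |
| 0.8 SD at both visits, skewed bounded | 5% | 80% | 5% | 64% |

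Monte Carlo standard errors are about 0.3 percentage points near 5% and 0.6 near 80%.

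The both-visits scenario is not far-fetched: T1 follows the training, and section 10.4 expects a better outcome already at cast removal. With the effect at T2 only, power is similar, yet the interaction and T2 rank tests reach different verdicts in 23% of trials.

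**5. Type I error.** Across normal, bounded and lognormal data:

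- Switch to one pre-specified Mann-Whitney test at T2: 4.9 to 5.2%.
- Mann-Whitney at both visits after a switch, either one counting: 6.3 to 9.1%.
- Free choice between the interaction test and Mann-Whitney at T2: 8.8 to 9.7%.

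**6. Power from adjustment.** Neither the covariate R² nor a 0.7 SD shift is in the documents; both are assumptions. At 26 per arm, 0.7 SD and normal residuals, a linear model with one covariate has 74, 77, 83 and 89% power at R² of 0.1, 0.2, 0.3 and 0.4, against 67 to 69% for Mann-Whitney. With six to eight covariate columns and R² = 0.1 it has about 65 to 68%, against 66 to 69%. At the plan's 0.20 SD, all versions lie between about 10 and 15%.

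**The case against.** The strongest reply is that section 9.3 is not itself an adjusted model with a single target. It lists only group and time, promises a difference at each visit, and the Summary describes a post-test only design. A per-visit group comparison is thus already one stated aim, and the absence of covariates from the model is a separate gap between 7.1.3 and 9.3. This stands. It means the switch cannot be said to discard a clearly specified adjusted analysis. It does not supply the missing trigger, visit or contrast.

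A reader might go further in four ways that the documents do not support:

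- **That the switch inflates type I error.** A single pre-specified rank test at T2 keeps it near 5%. The higher rates need further choices that the plan leaves open but does not prescribe.
- **That a switch somewhere is almost certain.** Counting 13 variables (PRWHE, six ROM, four grips, two VAS) at four checks each gives 1 − 0.95⁵² = 93%. This rests on an assumed trigger and on independence between related measures in the same patients, and 12 of the 13 variables are secondary.
- **That the switch costs substantial power.** The gain from adjustment depends on R² and the number of covariates, and may be nil.
- **That the time contrast is necessarily lost.** Mann-Whitney on change scores would retain a form of it; section 9.2 simply does not say so.

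Section 9.1 does report PRWHE means and SDs, so a raw difference could be read off, but without an interval.

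**Conclusion.** The point holds. For the primary PRWHE, section 9.2 makes the choice of test depend on an undefined assessment of the trial data, and its alternative branch cannot carry the time factor or the promised covariates and has no planned estimate with an interval. The consequences are a changed hypothesis and room for analyst discretion. Under the stated assumptions, the same data-generating truth leads to rejection in about 5% or about 79% of trials depending on the branch, and normal data alone would trigger the switch in about 19%. Those sizes depend on the assumed Shapiro-Wilk trigger, a correlation of 0.5, the 0.8 SD effect and Mann-Whitney being applied at T2. The defect in the text does not depend on them. No general claim of type I inflation or lost power is warranted.

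**What to change.** Delete the normality switch for PRWHE, ROM, grip strength and VAS. Analyse each with one pre-specified linear repeated-measures model whatever the normality result: group, time, group-by-time, and those 7.1.3 covariates measured before the intervention starts. Write the covariates into 9.3. Age, fracture type and the VMIQ score qualify. Occupation and sport qualify if recorded before training. Use of the casted hand follows allocation and could be affected by the training, so it should not be adjusted for.

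Name the primary contrast and visit, and reconcile them with section 4.4. If the interaction stays primary, the plan should acknowledge that it does not detect a benefit already present at T1 and unchanged at T2. If a group difference at a visit is chosen, the sample size must be recalculated for it.

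Report the difference in points with a 95% CI, use a bootstrap or permutation p-value if residuals are skewed, and keep Mann-Whitney as a sensitivity analysis at a named visit. SODA can stay as planned: it is assigned to Mann-Whitney in advance as ordinal, so its test is not data-dependent.

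The cost is wording, with no extra visits or data. The downside is a few degrees of freedom, and slightly less power if residuals are strongly skewed and the covariates explain little (74% against 78% in a gamma-residual simulation with one covariate at R² = 0.1 and a 0.7 SD shift). Keeping the interaction as primary leaves the calculated 52 unchanged.

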7.2 Randomization, blinding and treatment allocation

Potential participants are randomly allocated to the experimental or control group before the start of the study, i.e. before inclusion. In this way, the potential participants allocated to the control group can receive other information about this study than potential participants allocated to the experimental group. This is done to prevent occurrence of the bias that might be present when the patients in the control group are aware of the working mechanism of motor imagery, and its potential benefits. When the patients in the control group know that they participate in a study that is conducted to determine whether motor imagery can promote the recovery after DRF, it is possible that they perform motor imagery during the immobilization, or pay more attention to their injured hand as normal. Such bias cannot be detected and may severely confound the results of this study. Therefore, we decided to keep the patients in the control group ignorant.

Because randomization is performed before inclusion, it is likely that some patients will decide not to participate, reducing the number of participants in that group. The experience of 2.5 years inclusion teaches us that the response rate to participate is different for each group (experimental group 35%, control group 62%). Therefore, the number of patients who will be asked to participate is controlled for this difference. This means that more patients are allocated to the experimental group, than to the control group. The random allocation is performed with remaining equal group sizes, and equal distribution of the different fracture types (intra-articular vs. extra-articular distal radius fractures).

The randomization process is done using PASW Statistics 18. Subject numbers are randomly allocated to the experimental or the control group. The order in which the patients receive their initial treatment determines their subject number. There is no blinding of the patients, nor the researcher is blinded.

Based on national statistics concerning the diseases and injuries diagnosed on a yearly basis, it is expected that 6-7 DRF-patients will be treated in the UMCG every week, and 2-3 of them will be women of 45-75 years of age (58).

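### Section 9.3 specifies a MANOVA with group and time only, section 7.1.3 promises six covariates, and the combined model is never written down

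*Combined protocol and SAP*

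**What the plan says.** Section 9.3 describes the test of the hypothesis: "With use of a MANOVA, the difference between the experimental and control group will be determined for each measurement time and for each variable". It continues: "There are two factors included in the analysis", a between-subject factor for group and a within-subject factor for time. It names no covariate and does not refer back to 7.1.3. Section 9.1 uses the potential confounders only to describe the patients.

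In section 7.1.3 the confounders "are age, motor imagery ability, type of fracture, occupation, sport activities and involvement of their casted hand in activities". Their role is stated without condition: "The confounding factors will be included in the statistical analysis as covariates to control for their influence". Neither section gives coding, says whether covariates are crossed with time, or says which contrast on the PRWHE is primary.

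Section 7.2 says that allocation aims at "equal distribution of the different fracture types", meaning intra-articular against extra-articular.

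Section 9.2 assigns the Mann-Whitney U test to non-parametric data and adds: "This test is also used when the data is not normally distributed". That test carries no covariates. The sample size calculation in 4.4 has none either.

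**The concern.** Two competent analysts could follow this protocol and report different primary p-values. One would fit 9.3 as written, without covariates. The other would add the 7.1.3 list. A third could find the PRWHE non-normal and use a Mann-Whitney test, which drops all adjustment.

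The choice matters more here than in a blinded trial. Section 7.2 says that neither patients nor researcher are blinded, and 9.4 plans an interim look at the effect on every outcome. The people choosing the model may already know which way the results point.

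Each section also has a fault of its own if taken literally:

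- **9.3** leaves out the factor used to balance allocation.
- **7.1.3** adjusts for involvement of the casted hand, which is behaviour during the cast period. Section 7.2 itself worries that knowing about imagery could make patients attend more to the injured hand. If training changes this behaviour, adjusting for it can remove part of the treatment effect.
- **7.1.3** also includes occupation and sport with no coding, so the number of model terms is open.

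**Working it through.** **1. The plan's own figure.** Inputs from section 4.4: effect size f = 0.20 as entered, alpha 5%, power 80%, 2 groups, 2 measurements, within-between interaction, other settings default. The default values are not printed; I assume correlation 0.5 and sphericity 1.

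λ = f² × N × m / (1 − ρ) = 0.04 × 52 × 2 / 0.5 = 8.32, with 1 and 50 degrees of freedom. Power is 80.7%, and 52 is the smallest even N reaching 80%. The figure reproduces from a model without covariates. Removing six degrees of freedom for covariates that explain nothing, and ignoring chance imbalance, leaves 80.5%, so N stays at 52.

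**2. Error if the choice stays open (group contrast at one visit).** Let R² be the share of outcome variance explained by the covariates. The documents give no value; I assume 0.10 to 0.25. Under the null hypothesis the unadjusted and adjusted z statistics have correlation √(1 − R²). The chance that at least one exceeds 1.96 in absolute value is 1 − P(|Z₁| < 1.96 and |Z₂| < 1.96).

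| Assumed R² | Correlation | Either test significant |
|---|---|---|
| 0.10 | 0.949 | 6.48% |
| 0.25 | 0.866 | 7.34% |

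Simulation of the T2 contrast with 26 per arm and three covariates agrees within about 0.3 percentage points.

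**3. Precision at T2 with three covariates.** Adjustment multiplies the residual variance by (1 − R²). Chance imbalance multiplies the variance of the estimate by about (N − 3)/(N − 3 − p) = 49/46 = 1.065 for p = 3.

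- R² = 0.10: unadjusted/adjusted SE = 1/√(0.90 × 1.065) = 1.02; equivalent N = 52/(0.90 × 1.065) = 54.2.
- R² = 0.25: 1/√(0.75 × 1.065) = 1.12; equivalent N = 52/(0.75 × 1.065) = 65.1.
- R² = 0: the adjusted SE is larger by √1.065 − 1, about 3%.

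Simulation gave the same SE ratios and an equivalent N of about 55 to 66.

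**4. Short list or long list.** Three covariates pay for themselves once R² exceeds 1 − 46/49 = 6%. Six need 1 − 43/49 = 12%. In a simulation with six covariates on the change score at N = 52, adjusted power was 79.1% at R² = 0.10, against about 81% unadjusted.

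**5. The group-by-visit interaction.** With two visits and complete data, this test is a comparison of T2 − T1 changes. A covariate that is constant over time and enters only as a main effect cancels from the change. In a random-intercept fit with three such covariates at N = 52, the interaction estimate was −2.4615 with SE 3.738, both with and without them. So steps 2 and 3 do not apply to the interaction in that form.

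They return once covariates are crossed with visit. With six crossed covariates, the either-test error was 7.1% at R² = 0.10 and 8.0% at R² = 0.30.

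**The case against.** The best defence is that there is only one model. Section 7.1.3 is unconditional, 9.3 counts factors rather than covariates, and a covariate is not a factor. On that reading the two sections together describe a MANCOVA. This stands to the extent that a reader who infers a flat contradiction, or two rival planned primary tests, goes beyond the text: no section plans an unadjusted primary test. But neither does any section state the merged model, its coding, its terms with time or its primary contrast, so the choice remains open.

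A reader might also infer that fracture type is never adjusted for. It is on the 7.1.3 list and is missing only from 9.3. The factor may even have a single level, because 4.3 has an exclusion for intra-articular, comminuted fractures that can be read in more than one way. Balance is also set before consent, with acceptance of 35% and 62%, so it is not assured among enrolled patients. The harm from omitting this one factor therefore cannot be sized.

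Taking 1/(1 − R²) alone would give an SE penalty of 5% to 15% and an equivalent of 58 to 69 patients. That ignores the cost of estimating the covariate effects (step 3).

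Finally, it is fair to say that the interaction sized in 4.4 is untouched by main-effect covariates. But 9.3 also speaks of differences at each measurement time, and for those the choice matters.

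**Conclusion.** The point holds as an unstated model, not as a contradiction. If the adjusted or unadjusted choice is left until the data are seen, the two-sided error for a per-visit group contrast is about 6.5% to 7.3%. At T2 the unadjusted SE is about 2% to 12% larger than with three covariates, an equivalent N of about 55 to 66. Both ranges rest on an assumed R² of 0.10 to 0.25, and the error range also assumes that whichever test is significant is reported.

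There is no such effect on the group-by-visit interaction when covariates are main effects only. A reader might infer that the sample size is undermined; adding covariates does not change the planned 52.

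The risk from adjusting for casted-hand involvement is separate from these figures and could bias the estimate. The documents give nothing from which to size it.

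**What to change.** In 9.3:

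- Name one primary PRWHE contrast: either the group difference at a stated visit or the group-by-visit interaction.
- State one primary model: group, visit, group-by-visit, fracture type, age and internal VMIQ score, with the coding given. If the contrast is the interaction, add covariate-by-visit terms.
- Drop fracture type if sections 4.3 and 7.2, once reconciled, leave only one type.
- Make the two-factor model without covariates a sensitivity analysis.

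In 7.1.3, use the same list. Take casted-hand involvement out of the covariates, giving the reason: it arises after allocation and may respond to training. Keep it, occupation and sport as descriptive variables. The VMIQ is also completed after allocation, but before the imagery instructions, so it cannot reflect the training; say so.

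In 9.2, state that for the PRWHE the Mann-Whitney test is a sensitivity analysis, not a replacement that depends on how the data look.

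The cost is wording, since the variables are already planned for collection, plus a few degrees of freedom out of about 50. If the covariates explain nothing, the SE rises by about 3%.

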1.3 Hypothesis

[figure not shown]
We hypothesize that motor imagery training during the immobilization period improves functional outcome, specified as an increase in function, dexterity, grip strength and range of motion, and a decrease in pain.

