6.7 Preparation and labeling of Investigational Medicinal Product

6.8 Drug accountability

7. METHODS

7.1 *Study parameters*

Based on literature about the outcome following a DRF (19-24), and experts' opinions, we decided to use 5 outcome measures. The main outcome measure is function. Other outcome measures used are the range of motion, grip strength, dexterity, and pain.

7.1.1 *Main study parameter/endpoint*

Research has shown that DRF-patients suffer more on long term from function restrictions than pain (15,16). Therefore, function is the main outcome measure. Function is measured using the Patient Rated Wrist/Hand Evaluation (PRWHE). This instrument is developed to measure disability during usual and specific activities, and it also documents pain and aesthetics. The PRWHE is derived from the PRWE and contains some extra questions about aesthetics. Because the PRWHE retains the originally validated questions, format and scoring system of the PRWE, it can be treated as the PRWE (59). A study that critically reviewed the available outcome assessment tools, showed that the PRWE is the most responsive instrument to measure outcome in DRF-patients (60). The PRWE is a self-rated questionnaire, and its mean completion time is 4 minutes (61). It consists of 15 questions, divided in 3 domains; pain, functional activities, and usual activities. The patients have to rate the severity of their pain or disability in different situations. The final score of the PRWE and PRWHE lies between 0-100, where 0 represents the best and 100 represents the worst outcome. The PRWE is found to be reliable and valid, and therefore provides a simple and quick method to measure patient-rated pain and disability (61).

7.1.2 *Secondary study parameters/endpoints*

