Secondary outcome measures are dexterity, active range of motion, grip strength, and pain. The Sequential Occupational Dexterity Assessment (SODA) is used to determine dexterity. The SODA is a valid and reliable instrument that measures bimanual dexterity during activities of daily living (68). The SODA consists of 12 tasks, and it takes 20 minutes to complete it. The performance on the tasks is scored by the experimenter. The score for each task is build up by two different components. One component concerns how the task is performed, and the other component concerns the difficulty the patient experiences during the execution of the task. For some tasks, only one hand is scored, while for other tasks both hands are scored. The final score

ranges from 0-108, where 0 means that the patient is unable to perform any of the tasks, and 108 means that all tasks were performed as requested without any difficulty (68).

Range of motion (ROM) is determined using a digital goniometer. Because unrestricted movement is essential for normal function, wrist movement in all directions is measured; flexion, extension, radial deviation, ulnar deviation, pronation and supination. The literature available concerning the amount of measurements needed to provide reliable outcomes, is contradicting (69). Some researchers have found that only one measurement is sufficient (70), whilst others have found that the average of several measurements is more reliable than one measurement (71). It is recommended to use the average of multiple measurements in the ROM that shows large variation or a systematic increase (69). We repeatedly measured the different ranges of motion, and this provided consistent results. Based on this we decided to use a single measurement of each aspect of ROM (i.e. flexion, extension, abduction, adduction, supination, and pronation). To control for within-group variability, ROM is measured on both hands.

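### PRWHE is named as primary, but section 9.3 tests every variable at every visit at an unadjusted 5% and does not say which result decides, so 5% is not the plan's error rate

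*Combined protocol and SAP*

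**What the plan says.** Section 1.3 hypothesises that the training "improves functional outcome, specified as an increase in function, dexterity, grip strength and range of motion, and a decrease in pain". Section 2 sets the objective over the same five domains.

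The plan does rank its outcomes. Section 7.1 states "The main outcome measure is function". Section 4.4 treats PRWHE as the primary variable and bases the sample size on it alone. The Summary and section 7.1.2 list dexterity, range of motion (ROM), grip strength and pain as secondary.

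Section 7.1.2 splits three of the secondary domains further. ROM covers "flexion, extension, radial deviation, ulnar deviation, pronation and supination", grip strength covers "grasp, tip pinch, key pinch, and three-jaw chuck pinch", and pain has two VAS scales. All outcomes are measured twice, at cast removal (PRWHE by telephone one day later) and two weeks after it.

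Section 9 does not carry the ranking over. Under the MANOVA in 9.3, "the difference between the experimental and control group will be determined for each measurement time and for each variable", and "The hypothesis is tested using two-tailed tests, with a significance level of 5" per cent. Section 9.2 adds: "The non-parametric data are analyzed using a Mann-Whitney U test for each variable". Section 9.1 classes SODA as ordinal, so dexterity takes this second route, as does any variable that is not normally distributed.

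**The concern.** The 5% is attached to the hypothesis, and the hypothesis spans five domains. The plan gives no decision rule: it does not say whether PRWHE alone decides, at which visit, or by which contrast, nor how many domains must show a difference. Several tests, each at 5%, could then be brought forward in answer to one question.

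At stake is the credibility of a positive result. Neither patients nor the researcher are blinded (section 7.2), and 52 patients are planned. If PRWHE shows a difference at one visit only, or an isolated secondary measure is significant, nothing in section 9 says whether the trial has succeeded.

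**Working it through.** **Inputs from the documents.** Two-sided 5%, no adjustment (9.3). Two visits (3, 7.3, 10.4). Five outcome measures (7.1). Separate measures: 1 PRWHE + 1 SODA + 6 ROM directions + 4 grips + 2 VAS scales = 14 (7.1.1, 7.1.2). Total sample size 52 (4.4).

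**Assumed.** The correlation ρ between test statistics is not given. It is varied from 0 to 0.9 and taken as common to all tests.

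**The plan's own figure.** Section 4.4 uses a repeated-measures ANOVA, within-between interaction, with effect size 0.20, α = 5%, 80% power, 2 groups and 2 measurements. With λ = f²·N·m/(1 − r), f = 0.20, N = 52, m = 2 and r = 0.5 (assumed software default), λ = 0.04 × 52 × 2 / 0.5 = 8.32 on (1, 50) degrees of freedom. Power is 80.7%, so 52 reproduces. The calculation therefore supposes one PRWHE contrast at 5%. Whether 0.20 is the right input is a separate matter.

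**How many tests section 9 allows.**
- PRWHE only, each visit: 2.
- One test per domain, each visit: 5 × 2 = 10.
- Each measure, each visit: 14 × 2 = 28.

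None of these counts includes the group-by-time interaction, the measurements on both hands, or the interim analysis of all five domains in 9.4.

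**Formulas for at least one p < 0.05 with no true effect.**
- Independent: 1 − 0.95^k. For k = 2, 10 and 28 this gives 0.0975, 0.401 and 0.762.
- Common correlation: 1 − E[{Φ((1.96 − √ρ·U)/√(1−ρ)) − Φ((−1.96 − √ρ·U)/√(1−ρ))}^k], with U standard normal, by numerical integration.

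| Tests | ρ = 0 | 0.3 | 0.5 | 0.7 | 0.9 |
|---|---|---|---|---|---|
| 2 (PRWHE, two visits) | 9.8% | 9.5% | 9.1% | 8.3% | 7.0% |
| 10 (five domains) | 40.1% | 35.1% | 28.7% | 21.3% | 12.8% |
| 28 (all measures) | 76.2% | 64.1% | 49.1% | 33.0% | 16.9% |

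**In favour of training only** (drop the second Φ term; a single test has 2.5%):
- 10 tests: 1 − 0.975^10 = 22% at ρ = 0; 11% at ρ = 0.7.
- 28 tests: 1 − 0.975^28 = 51% at ρ = 0; 17% at ρ = 0.7.

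**Check with a less uniform structure.** Simulated t tests with 26 per arm used assumed correlations of 0.5-0.8 within domains, 0.3-0.6 between domains and 0.6-0.8 over time. They give 39-61% for the 28 tests and 7.9-9.1% for PRWHE at two visits.

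**The case against.** The strongest reply is that the plan already has a hierarchy. PRWHE is primary, it alone sets the sample size, and the rest are called secondary. A reader who follows those labels would judge the trial on PRWHE, and at one visit that carries exactly 5%. This stands as far as it goes, and it makes the larger figures inapplicable to a PRWHE-only claim. It does not close the gap, because no visit or contrast is named: PRWHE alone still carries about 8-10%.

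A second reply is that the MANOVA protects the per-variable tests. No such condition is stated, and SODA lies outside the MANOVA. If a gate at each visit is read in, two MANOVAs and two SODA tests give 1 − 0.95^4 = 18.5% if independent, when nothing has an effect.

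Two stronger readings are tempting and are not supported. A reader might infer that the hypothesis counts a gain in any single domain as success, so that one pinch strength would prove it. Section 1.3 joins the domains with *and*, not *or*. If all five had to succeed, with one test each at one visit, the error rate would be at most 5%. The text does not state that rule either; what it leaves is ambiguity. A reader might also take 28 as the plan's settled number of tests and 76% as its error rate. Section 7.1 speaks of five outcome measures, and section 9 never says that each direction or grip is tested separately. Zero correlation is also implausible for related measures in the same patients.

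**Conclusion.** The concern holds as a gap between the outcome hierarchy and the analysis section. Outcomes are ranked in 4.4 and 7.1, but section 9 does not say which single result, at which visit and by which contrast, carries the 5%. The size depends on the reading: least for PRWHE alone, more for five domains, most if every measure is tested. Under all three the chance of a false positive exceeds 5% at every correlation examined, including 0.9. The counts follow from the documents, but the correlations are assumptions, and the two larger figures apply only if a result outside PRWHE may support the effectiveness claim, which the plan neither allows nor excludes.

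**What to change.** Amend section 9.3, before any further look at outcome data by group, to name one PRWHE contrast as the only confirmatory test at two-sided 5%, and state that the claim of effectiveness rests on it. The contrast may be the group difference at one named visit or the group-by-time interaction. It must match section 4.4, which uses the interaction; choosing a single visit means redoing that calculation. The timing matters because section 7.2 reports 2.5 years of inclusion and an unblinded researcher, and 9.4 plans an interim analysis of all outcomes.

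Label the remaining PRWHE comparison and all dexterity, ROM, grip and pain results as secondary or supportive. Report them as estimates with confidence intervals, and state that none can support the effectiveness claim on its own. Align the wording of 1.3 and 2 with this.

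Holm adjustment over one pre-named summary per secondary domain is an optional addition on which statisticians differ.

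The cost is an amendment to the text, with no added patients or visits if the interaction is kept. The small downside is that an isolated secondary finding can no longer be presented as proof of effect.
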